6.4.2. Preventative health care

In the household survey we measure the following preventive health behaviors:

- For women pregnant in the last 12 months:

% getting at least one or all recommended prenatal care visits

· % receiving a tetanus vaccine

• % delivering (including C-sections) in a public facility

% delivering (including C-sections) by a trained medical professional

- For households with children under age 6:

• % receiving at least one recommended immunization

• % receiving each recommended immunization (polio, tetanus, etc.)

- For all households :

• % of households that boil or otherwise clean or treat drinking water (for prevention of diarrhea)

• % of households that keep water jugs covered (for prevention of dengue and diarrhea)

Some measures may be gathered by direct observation of household survey enumerators.

6.4.3. Knowledge of appropriate preventative health carebehavior

Because insurance is likely to provide increased exposure to public health facilities and thus to public health information provided at these facilities, family members' knowledge of preventive health behavior may be impacted. We will use the household survey to measure the following indicators of knowledge of appropriate preventive health behavior:

• % of respondents with knowledge of:

Appropriate infant and child care (including immunizations)

· Methods to prevent dengue

Methodology for Objective 2: The determinants of takeup of health insurance

A. Statistical Methods

A major issue that voluntary insurance programs must contend with is adverse selection, whereby people who anticipate high health care costs are more likely to buy health insurance. Such self-selection increases utilization and costs. The resulting higher premiums and lower take-up can reduce or eliminate the risk-pooling aspect of health insurance.

However, another group of people that may buy health insurance are those who are very risk averse with both their health and their finances. These people may buy insurance to protect themselves financially, and may also be very healthy. If that is the case, this positive selection may balance out adverse selection and allow an insurance company to pool risks and thus remain financially viable.

Another important issue is how well insurance is reaching its target audience. SKY currently has low take-up, and one concern is that households that could be benefiting from the program are failing to enroll. A household may decline SKY due to many reasons, including low perceived risk of a negative health shock, infrequent use of health services, little past experience with negative health shocks or large health expenditures, low perceived quality of public health facilities, inconvenience of public health facilities, low trust of institutions in general or SKY in particular, high value given to current consumption, low ability to pay for insurance premiums, high ability to pay for health care or to insure themselves in other ways, preferences against trying untested products and so forth.

Understanding the causes of low take-up will allow us to draw conclusions regarding whether households that do not buy SKY are making reasonable decisions or if SKY should explore ways to insure these households.

To measure selection into insurance, we will run five sets of analyses. First, we will look at average baseline characteristics of households that buy SKY and compare them to those who don't buy SKY. We will also run a logistical regression to determine the impact of each indicator on the purchase of insurance (where decision to purchase (0 or 1) is on the left- hand side and household and health facility quality characteristics are on the right-hand side of the equation).

Second, we will compare characteristics and average health care utilization of households that buy SKY at different prices, to examine whether a lower price induces more risk pooling (that is, attracts a healthier applicant pool).

Third, we will use external sources of data—the Cambodia Demographic Health Survey (DHS) and 2008 Census —to compare the profiles of village members who attend SKY village meetings and of SKY members to the general population (at the national, provincial and possibly district level). In the household survey our demographic measures (household size and members' age and sex) and some of our health (e.g., body mass index, that is, weight for height) and socioeconomic status (e.g., education) data are directly comparable to the DHS.

Fourth, we will examine selection using SKY data on membership and member utilization of health facilities. To

illustrate the possibilities, in 2007 all but one of the SKY members who had used a health center at least once renewed their membership, which was a far higher renewal rate than among those who had not used a facility at least once. This is a simple analysis using incomplete data, but illustrates the potential for such data to provide important insights into who is keeping and who is dropping insurance.

Finally, the Village Monograph will give us an in-depth qualitative study of how households make the decision to purchase insurance, how they use health facilities differently when covered by it, and how they decide to renew or drop insurance—all of which help us understand selection into the insurance market.

B. Predictors of Take-up

We will use the following measures that are collected using the household survey (described above) to predict take-up of SKY insurance:

• Wealth/income indicators (e.g., a wealth index created by asset ownership)

 Demographic characteristics of the household (age of members, number of members, gender and age of head/primary decision-maker, etc.)

• Past health utilization of family members (as discussed in previous sections)

· Past experience with large health shocks or expenditure

 Health level of family members at date of purchase (as discussed in previous sections)

• Alternate means of health financing in the absence of insurance (access to loans, etc.)

In addition, the household survey will include measures of the following constructs that may affect take-up. When feasible, we ask who in the household was influential in deciding to buy or decline SKY insurance and will pose these questions to someone who was influential. We will measure: • Perceptions of public health care quality

• Self-perceived predicted health risk/predicted need for health care for each household member

• Cautiousness with money (financial risk aversion), as measured by a series of hypothetical lottery games

• Cautiousness with health (health risk aversion), as measured by a series of questions regarding risky health behaviors

• Willingness to try new products

• Personal discount rate/preference for present consumption, as measured by a series of hypothetical games that trade present for future consumption

• Trust of institutions (government, NGOs, etc.)

We will also measure health care quality using the household survey and GRET's quality assessment, as described above. Finally, we will use village maps and data from the village leader to calculate distance from public and other health facilities.

Methodology for Objective 3: Effects of health insurance on public health facilities

We will examine several measures of public health center quality in the household survey:

• Perceptions of public health facilities (distinguishing whether the respondent has been to public facilities)

For those who have been to public facilities, reports on:

o Availability of equipment and supplies (including drugs) o Staff treatment of patients

o Staff and facility observance of official work hours

o Under-the-table payments in addition to official user fee payments

Surveys of member facilitators will provide longitudinal data on:

• Staff and facility hours (including observance of official hours)

 Completeness (and potentially, accuracy) in recordkeeping · Availability of equipment and drugs

Qualitative research will use in-depth interviews to examine how SKY has affected health facilities. Questions will cover facility equipment, supplies, and other measures of overall functioning. In addition, staff will be asked about their salaries, hours, and thoughts on SKY. Health care providers will also be asked about the care-seeking behaviors of SKY versus non-SKY members. For example, we will ask about the number of inpatient versus outpatient visits, severity of illness at visits, and days spent in the hospital for both SKY members and non-SKY members.

We will also look at trends in the quantitative measures of health center quality (from the surveys of households and of member facilitators). SKY members may increase their expectations of health center quality once they join SKY. Thus, we will emphasize attitudes of low-coupon households. SKY membership will be fairly low in this group, so any effects of SKY membership should not bias results substantially.

Methodology for Objective 4: Contribution to the general body of knowledge

Currently, several countries around the world are considering the development of health insurance programs, yet little is known about the effects of health insurance on outcomes of interest. The evaluation of SKY will thus serve as a global public good. Rigorously documenting the program's impact-both what works and what does not-will allow Ministries of Health, donors, and policymakers around the globe to learn from SKY's example. The results of this evaluation will serve as an important tool as governments and aid organizations determine whether voluntary health insurance represents a viable strategy to meet their health goals. In this way, GRET's initial investment in health insurance in Cambodia may multiply to improve health and economic outcomes in developing countries around the world.

The following outputs will allow us to contribute to the general body of knowledge on health insurance, risk research, and development:

• Each year throughout the project, we will meet with Cambodian Ministry of Health officials and international donors to ensure that relevant questions are being answered.

• As data become available, we will produce reports on program impact and take-up of insurance.

- Reports will be produced in English and Khmer, and will be distributed to donors and Ministry of Health officials.

- Reports will also be posted online and will be publicly available.

• At the end of the project, a policy brief will be produced and distributed to Ministry officials, donors, and GRET, and will be posted online.

• Results will be presented at various seminars and venues:

- Once per year, we will present a paper on the evaluation at the Cambodian Socio-cultural Research Congress held at the Royal University of Phnom Penh.

- Results will be presented at academic and non-academic seminars and presentations.

Statistical Appendix

a. Instrumental Variables

We would like to estimate the effect of having health

insurance on health care utilization (or some other outcome). We might run a regression:

1) number of health center visits = $\beta_0 + \beta$ · has health insurance + controls + ϵ .

Here, β is the effect of health insurance on the outcome, number of health center visits, and ϵ is an error term representing individual variation from the average effect of health insurance on health center visits. β 0 is a constant, representing the number of health center visits when a household does not have health insurance. Contained in ϵ is any factor that we are not including on the right-hand side of the regression.

If buying health insurance were completely random (at least among people with similar observable control variables), then an Ordinary Least Squares (OLS) regression of the above equation would give us an unbiased estimate of β . In that case, owning health insurance will not be correlated with the error term, and we say that the correlation of health insurance and the error term is equal to zero, or E(health insurance * ϵ) = 0.

Unfortunately, it is likely that buying health insurance is correlated with unobserved factors such as poor health. In that case, having health insurance will be correlated with the error term, ε , which contains the effect of unobserved influences on number of health center visits. In other words, E (health insurance * ε) is not zero. Therefore, OLS regressions of (1) are biased, meaning that the estimation of β will contain the effect of other factors besides health insurance on health. Intuitively, if sick people both have many health center visits and buy health insurance more often, it will appear that insurance raises the number of health center visits even if the causal effect is zero.

We are running a lottery for coupons that reduce the price of insurance. Thus, we can run a first-stage regression:

2) health insurance = $\beta_0 + \alpha$ · high-value coupon for insurance + controls + u.

Here, "health insurance" is a variable equal to 1 if a household buys health insurance and 0 if a household does not buy health insurance, and "high-value coupon for nsurance" is a variable equal to 1 if a household wins a high-valued coupon for insurance, and 0 otherwise. The "controls" are any other characteristics that we believe

influence the purchase of health insurance. We can estimate α using a linear probability model (that is, OLS), although other functional forms are possible. We can use the estimated coefficients to predict p[^] ("p-hat"), the probability of having health insurance.

3) number of health center visits = controls + β_{2SLS} · p^A.

Now we can run a second-stage equation:*

As long as the coupon given in the lottery is uncorrelated with baseline health (or other determinants of health center visits), the two-stage least squares estimate β_{2SLS} will be an unbiased estimate of the true effect of health insurance on health center visits. This procedure is called two-stage least

squares or instrumental variables techniques, with the coupon value as the instrument.⁵

It might be simpler to think of the analysis in 2 pieces. We can run a non-causal reduced form equation (where Δ = change in a variable):

4) number of health center visits = controls + γ * high-value coupon for insurance.

Now the coefficient we care about is β , and can be estimated by:

 $\beta^{A} = \Delta$ health center visits / Δ insurance status

= (Δ health center visits/ Δ coupon value) / (Δ (insurance status) / Δ coupon value)

$$= \gamma^{\prime} / \alpha^{\prime}$$
.

That is, the ratio of the coefficient from the reduced form equation (4) (how coupons affect health center visits) to the coefficient from the first stage in equation (2) (how coupons affect insurance uptake) can tell us how insurance affects health center visits. Intuitively, assume coupons are distributed in random lotteries, and having a valuable one leads to a 50 percentage points higher probability of buying insurance. Moreover, assume households with coupon winners also have 1.5 extra health center visits per year (on average). Then it appears the causal link between buying insurance and visiting health centers = 1.5 more health center visits / 50% more insurance = 3 more health center visits for households with (exogenously) higher insurance.

A good instrument is correlated with the main variable of interest (in this example, health center visits) but not correlated with the error term of the main equation (health at baseline or anything else that predicts health center use).

⁵ Mathematical note: When unobserved health status at baseline (which is contained in the residual to equation 1, ϵ) is correlated with the purchase of health insurance (X), the OLS estimate of the true β is biased up:

 $E(\beta OLS) = \beta + \beta \cdot cov(\epsilon, Health insurance) / V(health insurance) > \beta$

Assume we have an instrumental variable Z (for example, a large-valued coupon) that is correlated with X but not with unobserved health status ϵ (that is, E(Z' ϵ) = 0). In words, Z is correlated with having insurance, but not other factors that affect health care utilization. Then we can create the instrumental variable estimate:

 $\beta IV = Z'Y / Z'X = Z'(\beta X + \epsilon) / Z'X$ (*)

The above equation is just the formula for calculating an IV or 2SLS coefficient. Taking expectations gives:

 $\mathsf{E}(\beta \mathsf{IV}) = \mathsf{E}\left[\left(\beta Z'X + Z'\epsilon\right) / Z'X\right] = \mathsf{E}\left(\beta Z'X / Z'X\right) + \mathsf{E}\left[Z'\epsilon / Z'X\right]$

Using the facts that $E(Z'\epsilon) = 0$ we have

E(βIV)= β,

so the IV estimate is not biased. One can show with lots of algebra that the two-stage least square estimate of β is the same as the starred (*) IV formula above.

Our lotteries provide such a rare instrument, and thus they provide us with causal estimates of the effect of health insurance on the outcome of interest. While there are many policy-relevant questions, the coupons answer only specific questions about those whose behavior is influenced by marginal reductions in insurance prices. Because coupons are only given to households that attend the village meeting, we will only be able to see the effect of insurance on those at the margin of purchasing insurance – not those completely uninterested. What the estimates will provide us is the effect of health insurance on those people that attended the meeting and were induced to buy insurance because of the largevalued coupon.

To illustrate the technique, here is a simplified version of the analysis that will illuminate the method.

(with illustrative numbers)	High-value coupon	No extra coupon value	Difference
Odds of insurance	0.6	0.1	Δ Pr(insurance) / Δ coupon value = 0.5
# health center visits per		1.07	Almost zero, as lottery tickets were randomized.
household prior to lottery			
# health center visits after lottery	2.5	1.03	Δ visits / Δ coupon value = 1.5
Change in lottery visits / affected			1.5 / 0.5 = 3
household			

Table 4: The effect of health insurance

The estimated causal effect we want is Δ health center visits / Δ insurance

Arithmetic tells us

 Δ health center visits / Δ insurance

= Δ health center visits / Δ coupon value / (Δ insurance / Δ coupon value) = 1.5 / 0.5 = 3.

That is, an extra half of those who won the coupon lottery purchased insurance, so we double the raw effect of winning a coupon on the number of health center visits to get the best estimate of the causal effect of insurance.

b. Difference-in-Differences

A very simple study of the effect of an intervention on an outcome might compare the outcome before and after the intervention. For example, one might compare average health care utilization of people before and after they purchase insurance.

Figure 1 shows average number of health care visits per year for two groups of people. Assume that Group A purchases insurance at the end of 1999. Group B does not purchase insurance. Comparing utilization of Group A before and after buying insurance would lead us to believe that insurance increases utilization by 3 visits per year (column 3, row 1).

Table 5: Utilization of Health Care Facilities
--

	1999	2001	Difference
Groupe A	2.5	5.5	3
Groupe B	1.7	3	1.3
Difference			1.7

However, this estimate ignores underlying trends in utilization that have been taking place between 1999 and 2001.

Therefore, to improve this estimate, one can use a method known as "difference in differences". The difference in differences technique uses a comparison group to establish a trend for health care utilization that takes place even without insurance. To find this underlying trend, we subtract 1999 utilization for Group B from 2001 utilization for Group B, which gives us an increase of 1.3 health care visits. If the trends between the two groups are identical, we can subtract the time trend from our initial estimate to get an improved estimate of the effect of insurance. To do this, we take the difference over time for Group B, 1.3. This gives us the "difference in differences", 1.7.

However, this simple difference in differences estimate still has a problem. It is possible that Group A and Group B have different trends over time. In our case, this may occur since people who buy insurance are a selected group, and thus may change in different ways over time. In that case, subtracting out Group B's trend over time will not correctly isolate the effect of insurance, since Group B's trend is not equal to Group A's trend. To improve upon this estimation, we want to ensure that trends over time between the two groups are equal. Randomization allows us to do this. If Group A is randomly assigned insurance and Group B is randomly selected not to receive insurance, trends between the two groups should be the same. In that case, subtracting out Group B's trend should correctly isolate the effect of insurance on Group A.

In relation to the current study, we are randomizing coupons, so that Group A randomly receives coupons and Group B does not. Figure 2 illustrates this idea. Notice that in 1999, utilization is around the same level. This is because, since coupons are randomized, the two groups should be initially about the same.

In this case, the effect we see when we look at the difference in differences, 2.6 in Figure 2, is the effect of receiving a large coupon, not the effect of insurance itself. That effect is known as the "intention to treat" (ITT), since we "intend" for people with large coupons to buy insurance. The "Methods" section of the main text gives an example of how to calculate the effect of insurance from the ITT effect.

Table 6: Utilization with	Coupon Randomization
---------------------------	----------------------

	1999	2001	Difference
Groupe A	2.5	5.5	3
Groupe B	1.7	3	1.3
Difference			1.7

The above calculations can also be written in regression form. For the effect of coupons on utilization illustrated in Figure 2, the regression equation is:

(5) utilization = β_0 + β^* coupon + γ^* 2001 + δ^* 2001* coupon + ϵ

Here, utilization is the number of visits, coupon is equal to

1 if the household received a coupon and 0 if not, 2001 is equal to 1 for the year 2001 and 0 for the year 1999, and 2001*coupon is equal to 1 if the observation is a household that received a coupon and is being observed in 2001. As for the coefficients, β gives the effect of any pre-existing differences between Group A and Group B. If coupons are perfectly randomized, this should be very small. γ gives the

effect of the time trend on utilization. The coefficient of interest is δ , which tells us how much the coupon increased utilization over and above any time trend or underlying differences between the groups. There are usually additional covariates (independent variables that influence utilization, such as household characteristics). They can be added to the right-hand side of the above equation.

Note that the difference in differences estimator described above uses group means to estimate effects. The above methodology can be used even when one does not have multiple observations of the same individuals over time. All that the above methodology requires is average outcomes for a treatment and control group, before and after the treatment.

c. Fixed Effects

Fixed effects are used when we have more than one measurement of a single unit of observation. In our case, we have baseline and follow-up measurements of the same households over time. Therefore, we can use household fixed effects to improve our estimates.

Suppose we randomly give some households coupons for insurance in 1999, but do not collect any data on these households until 2001. In that case, we have cross-sectional data only, meaning one observation per household. With this data, we can run a regression of health care utilization on coupon receipt, using our data from 2001:

(6) utilizationi =
$$\beta_0 + \beta^*$$
couponi + ϵi

In the above equation, the subscript i stands for households, so each observation is a household.

Suppose we had observations for a group of households in 1999 and for a different group of households in 2001. In that

case, we could use the difference-in-differences model described in equation (5), but we still do not observe the same household over time. This type of data is called a repeated cross-section.

Suppose now that instead of just having observations at one point in time, or at two points in time for different groups of households, we have observations on the same households both before and after they receive a coupon. This type of data is called panel data. In that case, we can use fixed effects to improve the accuracy of our estimates. Essentially, what we are doing is allowing each household to have a unique baseline level of utilization. Thus, the effect of insurance is assumed to be equal for each household, but the regression line represented by the basic regression equation is raised or lowered for each household (i.e., the intercept is different for each household).

For example, if we have panel data we can take our difference-in-differences estimate from equation (5) and add fixed effects. Below, i represents a household and t represents time.

(7) utilizationit = β_0 + β^* couponit + γ^* 2001 + δ^* 2001*couponit + household_i + εit

In the above equation, we use the difference-in-difference equation, but allow each household to have a unique (fixed) baseline level of the outcome. Essentially, what we are doing is including a variable representing each household. Thus, **household** represents not just one variable, but an entire vector of variables. Adding household fixed effects will give us a more accurate estimation of the variable of interest, δ in equation (7), since we are reducing variance due to fixed household differences.

As in equation (5), we can add additional variables to the

right-hand side of equation (7) that we think will have an effect on utilization. Fixed characteristics of households will be taken care of by the household fixed effects, but we can add household characteristics that vary over time.

d. Clustering

Finally, when we run the regression we will want to take into account clustering of observations. Clustering of observations occurs when certain observations are more similar to each other than other observations. For example, households that are located within the same village may be more similar, and may experience more similar shocks (economic, health, etc.) than households in a different village. In the same way, individuals who live in the same household may be more similar to each other than individuals in other households. If we do not correct for clustering, standard errors will appear artificially low, leading us to overestimate the accuracy of our coefficient estimates.

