3. To identify potential effects of health insurance on public health facilities (e.g., hours and drug availability; subjective and objective quality indicators).

 To contribute to the body of knowledge on health insurance in Cambodia and in developing countries more broadly.

3. Research Design

We will use a mix of qualitative and quantitative methods, including both in-depth interviews of SKY employees, health care providers and households and a large household survey.

The large household survey will measure the impact of insurance on rural Cambodians. To overcome the key obstacle to causal inference—that those who choose to purchase insurance typically differ in many observable and unobservable ways from those who do not—we will implement a randomized controlled trial that allows us to identify the impact of health insurance independently from all other factors that may affect a household's decision to take up insurance. No household will be denied access to insurance. Rather, by subsidizing the premium of a randomly selected group of households, we can estimate the effect of insurance on households without substantially altering the existing SKY program. The study design will also enable us to examine characteristics of the groups that buy or decline insurance at different prices. Using data from the baseline survey, we will examine the characteristics (in particular, health status and prior health care utilization) of those who choose to purchase health insurance at different prices. Using data from the follow-up survey, we will also compare the utilization rates of people who buy insurance at different prices, and compare the dropout rates of those who utilize facilities at different rates. Both techniques allow us to estimate the extent and nature of self-selection.

The randomized evaluation will be implemented as SKY visits villages to promote insurance. When the SKY program first rolls out into a region, SKY holds a village meeting to describe the insurance product to prospective customers. At

the end of each meeting, SKY will hold a Lucky Draw lottery in which a random subset of households receives coupons for discounts on the insurance premium.

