The randomization of premiums will provide a discount to some households. Of households that attend the village meeting, 20% of households, up to a maximum of 12 households per village, will win a coupon for 5-months free insurance in the first 6-month cycle, with the option to renew for a second 6-month cycle with a coupon for 3-months free. The remaining households in attendance at the meeting will be entitled to a coupon for a 1-month discount on insurance, which is the usual policy for the SKY program. SKY will be holding village meetings in Takeo, Kandal, and Kampot provinces over the course of the thirteen months from November 2007 to December 2008 (roughly the period during which the baseline survey will be administered). Table 1 shows an approximation of the distribution of the targeted sample across regions. The column "Total Meetings Held" indicates the number of village meetings SKY plans to hold in each district or province and "Total Lucky Draws" indicates the number of Lucky Draws held in the given district. The final column, "% of Villages Surveyed", indicates the approximate percentage of the sample that will come from each area. Note that we will hold Lucky Draws at most village meetings in 2008. We will only survey villages in which we hold a Lucky Draw.

				Total	Total	% of Villages	
				Meetings	Lucky	Surveyed	
				Held	Draws		
Takeo Province			128	128	51%		
Ang Roka village	s (older	villages)		32	32	13%	
Kirivong villages			48	48	19%		
Donkeo villages				48	48	19%	
Kandal Province	74	72	29%				
Koh Thom village	es			74	72	29%	
Kampot Province	50	50	20%				
Kampot villages				50	50	20%	
All Villages				252	250	100%	

Table 1: Targeted Regions

In addition to the randomized intervention, we will also be studying the effect of SKY on the quality and functioning of public health facilities. The fact that higher quality facilities are targeted by SKY means that there can be no valid control group in a longitudinal study, but we will use several methods to measure changes in health center quality over time that will allow us to gain some insight into the impact of SKY.

4. Sampling Strategy

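### Follow-up utilisation of buyers at different prices mixes who bought with how long they stayed covered, so it cannot be read as self-selection; the documents do not fix the direction of the bias

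*Protocol*

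**What the plan says.** Section 3 (Research Design) sets out two comparisons of buyers by price. One uses the baseline survey and looks at their characteristics ("in particular, health status and prior health care utilization) of those who choose to purchase health insurance at different prices"). The other uses later data: "Using data from the follow-up survey, we will also compare the utilization rates of people who buy insurance at different prices". Of the baseline and follow-up approaches together it concludes: "Both techniques allow us to estimate the extent and nature of self-selection".

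Methodology for Objective 2, A (Statistical Methods) repeats the plan: "we will compare characteristics and average health care utilization of households that buy SKY at different prices". The stated purpose is "to examine whether a lower price induces more risk pooling (that is, attracts a healthier applicant pool".

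The coupons are described in section 3. Large-coupon households "will win a coupon for 5-months free insurance in the first 6-month cycle". Their discount then continues at renewal, in the protocol's words "with the option to renew for a second 6-month cycle with a coupon for 3-months free". The others "will be entitled to a coupon for a 1-month discount on insurance, which is the usual policy for the SKY program"; no renewal discount is stated for them. Section 5.1 places the second survey round 12 months after baseline, so the interval spans both 6-month cycles.

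**The concern.** The two buyer groups face different prices twice: at purchase and again at renewal. The first difference is the one that Objective 2 wants to exploit. The second acts after purchase and can change how many of the following months a household is insured. Section 6.4 expects insurance to change care-seeking, so a difference in months of cover can produce a difference in use between groups that were equally healthy when they bought. Restricting the comparison to buyers does not remove this, and no section limits use to covered months or to the first cycle.

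At stake is the answer on risk pooling. If the follow-up comparison is taken at face value, an effect of insurance can be reported as a difference in who was attracted. The baseline and follow-up comparisons could also disagree, and the protocol gives no rule on which to believe.

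**Working it through.** **The plan's own counts (Table 2).** 250 meetings x 9.5 = 2,375 households per coupon group. Large-coupon buyers: 2,375 x 0.40 = 950. Sampled small-coupon buyers: 2,375 x 0.06 = 142.5, shown as 143. Total: 2,375 + 2,375 + 453 = 5,203, as stated. The comparison is therefore of about 950 buyers with 143 + 453 = 596. The protocol gives no renewal rate by coupon.

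**Premium months paid by a buyer (from the coupon terms in section 3).**

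| | Large coupon | Small coupon |
|---|---|---|
| First cycle | 6 - 5 = 1 | 6 - 1 = 5 |
| Second cycle, if renewed | 6 - 3 = 3 | 6 (no discount stated) |
| 12 months | 4 | 11 |

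The price gap persists in the second cycle: 3 months against 6.

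**Assumptions (none is in the documents).** Every buyer keeps the first cycle in full. A share r renews for the whole second cycle (rL for large-coupon buyers, rS for small-coupon buyers). Monthly use is k times as high when covered as when not. The true selection ratio, large to small, is 0.90, meaning that large-coupon buyers need 10% less care.

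**Formulas.**
- Covered months in 12: c = 6 + 6r.
- Use over 12 months is proportional to k x c + (12 - c) = 12 + (k - 1) x c.
- Ratio from cover alone: R = [12 + (k - 1) x cL] / [12 + (k - 1) x cS].
- Ratio read from the data: 0.90 x R.

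| rL vs rS | cL vs cS | k | R | 0.90 reads as |
|---|---|---|---|---|
| 0.6 vs 0.4 | 9.6 vs 8.4 | 1.5 | 16.8 / 16.2 = 1.04 | 0.93 |
| 0.8 vs 0.4 | 10.8 vs 8.4 | 3 | 33.6 / 28.8 = 1.17 | 1.05 |
| 0.5 vs 0.5 | 9.0 vs 9.0 | any | 1.00 | 0.90 |
| 0.4 vs 0.6 | 8.4 vs 9.6 | 1.5 | 16.2 / 16.8 = 0.96 | 0.87 |
| 0.3 vs 0.6 | 7.8 vs 9.6 | 3 | 27.6 / 31.2 = 0.88 | 0.80 |

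With k = 1, R is 1 whatever the renewal shares.

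**Four-week use.** Section 5.5 limits recall of small health problems to four weeks. If that window lies in the second cycle, cover in it depends on renewal alone, and R = [1 + (k - 1) x rL] / [1 + (k - 1) x rS]. For 0.6 vs 0.4 with k = 1.5, this is 1.3 / 1.2 = 1.08. For 0.8 vs 0.4 with k = 3, it is 2.6 / 1.8 = 1.44. A true 0.90 then reads about 0.98 to 1.30, a larger distortion than for whole-year use.

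**Use per covered month.** Within the first cycle the cover term cancels: (0.90 x k x cL / cL) / (k x cS / cS) = 0.90. The assumed selection ratio is recovered.

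**The case against.** **Direction.** A reader might infer that the comparison hides risk pooling, because cheaper renewal keeps large-coupon buyers insured longer. That is plausible for any one household, but the documents do not show it for the groups. Methodology for Objective 2, A reports that in 2007 members who had used a health centre renewed far more often than those who had not, while calling those data incomplete. A healthier large-coupon group could therefore lapse more, and the comparison would then exaggerate risk pooling. Section 2 also expects substitution from private to public care, so the effect of cover depends on which use is measured. This objection stands: only a bias of unknown sign can be claimed.

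**Size.** A reader might take the Statistical Appendix's 3 extra visits per insured year and divide by its 1.03 visits. The false difference is 3 x (6 x gap) / 12 = 1.5 x gap. Renewal gaps of 10 to 40 points give 0.15 to 0.60 visits, or 15% to 58% of 1.03. That base is wrong. Table 4 is illustrative, and 1.03 is the mean of a group of whom 10% are insured. The comparison is also between buyers. Even if 1.03 is taken as the uninsured level, small-coupon buyers renewing at 40% have 1.03 + 3 x 8.4 / 12 = 3.13 visits, and the false difference is about 5% to 19%.

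**Already covered.** The baseline comparison asks the same question and renewal cannot affect it. Follow-up use by price is one component of a broader selection analysis. This also stands and limits the point to that component.

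**Left to the SAP.** Section 3 speaks of rates, and a rate could have covered months as its denominator. An SAP, which is not shown, might say so. But the protocol itself states the inference to self-selection. Objective 2 speaks only of average utilisation, and the indicators in section 6.4.1 are per individual, household or incident. This does not rescue the comparison as written.

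**Conclusion.** The point holds for the follow-up utilisation comparison only. As written, it confounds selection at purchase with coupon-driven differences in cover, and the protocol's reading of it as self-selection is not secure. On whole-year use, a true ratio of 0.90 reads 0.93 to 1.05 if large-coupon buyers renew more, and 0.80 to 0.87 if they renew less. It stays at 0.90 if renewal is equal or cover does not change use. Renewal shares, k and 0.90 are all assumptions, so these figures show the range of possible distortion and are not an estimate. The documents do not support the conclusion that risk pooling will be hidden, or that Objective 2 as a whole is compromised.

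**What to change.** In section 3 and in Methodology for Objective 2, A:

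- Name the baseline comparison of health status and prior utilisation by price as the main test of selection.
- For use after purchase, compare buyers on use per covered month within the first 6-month cycle, from SKY membership and utilisation records.
- State that whole-year and four-week follow-up use by price will not be interpreted as selection.

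The baseline comparison and the use of SKY records are already planned, so this changes analysis wording and adds no fieldwork. The costs are real: a shorter window gives fewer visits and a wider interval, and SKY records may not capture private or traditional care, which the household survey does. The per-month measure also assumes that use while covered does not depend on how long the household stays within the first cycle. Restricting baseline use to dates before the village meeting is not proposed, because the survey description does not say that incidents are dated.
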